3.3.5 Treatment delivery technical factors

Treatment will be initiated within three weeks of the initial treatment planning simulation study. Treatment will be delivered with a minimal inter-fraction interval of 36 hours, and no greater than 84 hours between fractions.

Only photon (x-ray) beams with energies greater than or equal to 6MV are allowed. Tumors located within the lungs should be treated with energies of no greater than 10MV, except for specific beams where large soft tissue distances must be traversed to reach target. Dynamic conformal arcs and flattening-filter-free beams are acceptable. All dose calculations should

be performed with tissue heterogeneity corrections.

Image-guided therapy (IGRT) utilizing on-board cone-beam imaging is required for each fraction prior to delivery of treatment. Patients should be aligned to the visible target volume. In cases where soft tissue contrast is poor on CBCT imaging, fiducial markers should be utilized for more accurate setup.

3.4 Intervention Plan

3.4.1 Antiemetic Premedications and Supportive Care Medications

Antiemetic premedications should not be routinely administered prior to dosing of drugs. Symptomatic antiemetics may be administered at the Investigator's discretion. Palliative and supportive care for disease-related symptoms will be offered to all patients on this trial.

3.4.2 Bisphosphonates

The use of bisphosphonates (e.g., zoledronic acid) or denosumab is permitted if patient has been using them prior to the study for at least 1 month.

3.4.3 Dose Delay Criteria for Nivolumab and Ipilimumab

Dose delay criteria apply for all drug-related adverse events (regardless of whether or not the event is attributed to nivolumab and ipilimumab). All study drugs must be delayed until treatment can be resumed. Imaging studies and the collection of blood and tissue for correlative studies should continue as planned even if dosing is interrupted. Radiation treatment should continue if the treatment is unlikely to worsen adverse event.

Nivolumab and ipilimumab administration should be delayed for the following:

- Any Grade ≥ 2 non-skin, drug-related adverse event, with the following exceptions:
 - Grade 2 drug-related fatigue or laboratory abnormalities do not require a treatment delay
- Any Grade 3 skin, drug-related adverse event
- Any Grade 3 drug-related laboratory abnormality, with the following exceptions for AST, ALT, or total bilirubin:
 - If a subject has a baseline AST, ALT, or total bilirubin that is within normal limits, delay dosing for drug-related Grade ≥ 2 toxicity
 - If a subject has baseline AST, ALT, or total bilirubin within the Grade 1 toxicity range, delay dosing for drug-related Grade ≥ 3 toxicity
- Grade 3 amylase or lipase abnormalities that are not associated with symptoms or clinical manifestations of pancreatitis do not require a dose delay.

- Any adverse event, laboratory abnormality, or intercurrent illness which, in the judgment of the investigator, warrants delaying the dose of study medication

During cycles 1 and 2, both nivolumab and ipilimumab must be delayed at the same time. Following the up to 4 administrations of the induction combination therapy with NIVO/IPI, Dose 1 of maintenance nivolumab will begin 3 weeks after the 4th dose of induction therapy. If the 4th dose of induction therapy has not been administered due to treatment delays or the discontinuation of combination therapy because of primarily ipilimumab related side effects such as colitis, high grade diarrhea or hepatitis before Day113, that dose/doses will be omitted and maintenance dosing will begin.

The schema is noted in Figure 3.4.2 below.

[figure not shown]

Figure 3.4.2 Dosing/Treatment Schema for nivolumab/ ipilimumab plus SBRT

* Cycle 1 of maintenance will begin 3 weeks after the 4th dose of induction therapy or after Day 113 if the 4th dose of induction therapy has not been administered due to treatment delays.

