3.4.5 Criteria to Resume Treatment on Nivolumab and Ipilimumab

If the criteria to resume treatment are met, the subject should restart treatment at the next scheduled timepoint per protocol. However, if the treatment is delayed past the next scheduled timepoint per protocol, the next scheduled timepoint will be delayed until dosing resumes. If treatment is delayed > 6 weeks, the subject must be permanently discontinued from study therapy, except as specified in discontinuation section.

Subjects may resume treatment with study drug when the AEs resolve to Grade ≤ 1 or baseline value, with the following exceptions:

- Subjects may resume treatment in the presence of Grade 2 fatigue
- Subjects who have not experienced a Grade 3 drug-related skin AE may resume treatment in the presence of Grade 2 skin toxicity
- Subjects with baseline Grade 1 AST/ALT or total bilirubin who require dose delays for reasons other than a 2-grade shift in AST/ALT or AST/ALT or total bilirubin
- Subjects with combined Grade 2 AST/ALT AND total bilirubin values meeting discontinuation parameters should have treatment permanently discontinued.
- Drug-related pulmonary toxicity, diarrhea, or colitis, must have resolved to baseline before treatment is resumed.
- Drug-related endocrinopathies adequately controlled with only physiologic hormone replacement may resume treatment.

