3.4.6 Discontinuation Criteria for Nivolumab and Ipilimumab

Treatment with nivolumab and ipilimumab should be permanently discontinued for any of the following:

If treatment is delayed > 6 weeks, the subject must be permanently discontinued from study therapy, except as to allow for prolonged steroid tapers to manage drug-related adverse events. Prior to re-initiating treatment in a subject with a dosing interruption lasting > 6 weeks, the overall PI ([name]) must be consulted. Tumor assessments should continue as per protocol even if dosing is interrupted.

Dosing interruptions > 6 weeks that occur for non-drug-related reasons may be allowed if approved by the Investigator. Prior to re-initiating treatment in a subject with a dosing interruption lasting > 6 weeks, the Investigator must be consulted. Tumor assessments and

the collection of blood and tissue samples for correlative studies should continue as per protocol even if dosing is interrupted. Radiation treatment should continue if the treatment is unlikely to worsen the adverse event.

- Any Grade 2 drug-related uveitis or eye pain or blurred vision that does not respond to topical therapy and does not improve to Grade 1 severity within the pre-treatment period or requires systemic treatment
- Any Grade 3 non-skin, drug-related adverse event lasting > 7 days, with the following exceptions for drug-related laboratory abnormalities, uveitis, pneumonitis, bronchospasm, diarrhea, colitis, neurologic toxicity, hypersensitivity reactions, and infusion reactions:
 - Grade 3 drug-related uveitis, pneumonitis, bronchospasm, diarrhea, colitis, neurologic toxicity, hypersensitivity reaction, or infusion reaction of any duration requires discontinuation
- Grade 3 drug-related laboratory abnormalities do not require treatment discontinuation except:
 - Grade 3 drug-related thrombocytopenia > 7 days or associated with bleeding requires discontinuation
 - Any drug-related liver function test (LFT) abnormality that meets the following criteria require discontinuation:
 - AST or ALT > 8 x ULN
 - Total bilirubin > 5 x ULN
 - Concurrent AST or ALT > 3 x ULN and total bilirubin > 2 x ULN
- Any Grade 4 drug-related adverse event or laboratory abnormality, except for the following events, which do not require discontinuation:
 - Grade 4 amylase or lipase abnormalities that are not associated with symptoms or clinical manifestations of pancreatitis.

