 - Isolated Grade 4 electrolyte imbalances/abnormalities that are not associated with clinical sequelae and are corrected with supplementation/appropriate management within 72 hours of their onset
- Any adverse event, laboratory abnormality, or intercurrent illness which, in the judgment of the Investigator, presents a substantial clinical risk to the subject with continued nivolumab or ipilimumab dosing

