3.8 Immunotherapy Adverse Event Management

Early recognition and intervention are recommended according to the management algorithms; and in addition include ophthalmologic evaluations for any visual symptoms in order to evaluate for nivolumab or ipilimumab related uveitis.

Because of the potential for clinically meaningful nivolumab or ipilimumab-related AEs requiring early recognition and prompt intervention, management algorithms have been developed for suspected **pulmonary toxicity, GI toxicity, hepatotoxicity, endocrinopathy, skin toxicity, neurological toxicity, and renal toxicity**.

These adverse event management algorithms are included in the Appendix Toxicities.

3.9 Adverse events associated with Stereotactic Body Radiation Therapy (SBRT):

Common side effects (may occur in more than 20 % people receiving treatment; some may be serious): Fatigue, nausea, vomiting, skin reddening or sensitivity, mild pain, diarrhea, decreased appetite, lung scarring, temporary changes in blood work (blood counts or liver enzymes) without symptoms

Occasional side effects (may occur in from 4%- 20% people receiving treatment; some may be serious): Skin thickening or numbness, sores or ulcers near the cancer location, cough, shortness of breath, rib pain and/or rib fracture, abdominal pain, fever, irritation of the esophagus (swallowing tube); fracture or damage to the spine.

Rare side effects (may occur in 3 % or fewer of patients receiving treatment; may be serious): Irritation of the lining around the heart or the heart muscle; severe shortness of breath; irritation or damage to spinal cord or nerves; paralysis; damage to nerves in the chest or abdomen; damage to the esophagus, stomach, or intestines requiring hospitalization or surgery; irritation of the large blood vessels around the heart; coughing blood; irritation of the

voice box causing hoarseness or pain; jaundice; abdominal swelling; low blood counts; kidney damage; death.

There is also anticipated possible additive toxicities of irradiation during immunotherapy. Anticipated examples could include increased incidence of pneumonitis in irradiated lung fields and increased incidence of colitis if normal bowel is included in irradiated abdominal fields.

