4.3 Study Calendar

The Investigator may perform more frequent examinations than shown in Table below if clinically indicated. Data from such additional examinations are also to be reported in the eCRF.

* baseline visit and W1D1 can be combined	Screening	Baseline Visit*	Induction Phase Cycle ^a 1 and 2				Maintenance Phase Cycle ^a 3 and every subsequent cycle (8 weeks) (up to 2 years)		30 day Follow-up ^r (X1)	Follow-up Visits ^s (X2 and X3)	Survival Follow-Up ^t
	D -28 to 0	D-3 to D 1	W1D1* (C1W1)	W4D1 (C1W4)	W7D1 (C2W1)	W10D1 (C2W4)	W1D1	W5D1			
Informed consent	X										
Inclusion/Exclusion Criteria	X ^p										
Archival Tumor Tissue ^b	X										
Nivolumab ^c			X	X	X	X	X	X			
Ipilimumab ^d			X	X	X	X					
SBRT ^e			X ^e								
Medical history	X	X									
Physical assessment	X	X	X	X	X	X	X	X	X	X	
Vital signs ^f	X	X	X	X	X	X	X	X	X	X	
Height	X										
Performance status ^g	X	X	X	X	X	X	X	X	X	X	
Pulse Oximetry ^h			X	X	X	X	X	X			
EKG	X										
Adverse Events Assessment			X	X	X	X	X	X	X	X	
Concomitant Medications	X	X	X	X	X	X	X	X	X	X	
Disease Assessment ⁱ	X	every 6 weeks (\pm 1 wk) for the first 13 months from treatment and every 12 weeks (\pm 1 wk) thereafter, until disease progression is documented or treatment is discontinued (whichever occurs later)									
CBC with diff ^j	X	X ^q	X	X	X	X	X	X	X	X	
Comp Panel ^k	X	X ^q	X	X	X	X	X	X	X	X	

TSH, free T4, free T3 ^u	X	X ^q	X	X	X	X	X	X		X		
Pregnancy test ^l	X	X	X	X	X	X	X	X		X	X	
	Screening	Baseline Visit	Induction Phase Cycle ^a1 and 2				Maintenance Phase Cycle^a 3 and every subsequent cycle (8 weeks) (up to 2 years)			30 day Follow-up ^r (X1)	Follow-up Visits^s (X2 and X3)	Survival Follow-Up ^t
	D-28 to 0	D-3 to D1	W1D1 (C1W1)	W4D1 (C1W4)	W7D1 (C2W1)	W10D1 (C2W4)	W1D1	W5D1				
Hep B or Hep C ^m	X											
Research biopsy ⁿ	X				X					X		
Blood sample ^o	X				X					X		
Survival Follow-Up ^t												X

a. 1 cycle = 6 weeks
 b. Archival Formalin-fixed paraffin-embedded (FFPE) tumor tissue must be available for correlative studies (Note: Fine Needle Aspiration [FNA] and bone metastases samples are not acceptable for submission)
 c. Nivolumab is to be administered as an approximately 60-minute IV infusion. Cycle 1 of maintenance will begin 3 weeks after the 4th dose of induction therapy or after Day 113 if the 4th dose of induction therapy has not been administered due to treatment delays or the discontinuation of combination therapy because of primarily ipilimumab related side effects

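### Section 3.4.3 starts maintenance nivolumab after combination therapy is stopped for high-grade diarrhea or colitis, while Section 3.4.6 permanently stops nivolumab for the same events at Grade 3 or higher

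*Combined protocol and SAP*

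**What the plan says.** Section 3.4.3 covers patients whose fourth induction dose has not been given. One route into the rule is treatment delay. The other is stopping the combination for effects mainly due to ipilimumab, "such as colitis, high grade diarrhea or hepatitis before Day113, that dose/doses will be omitted and maintenance dosing will begin". The preceding sentence identifies maintenance as nivolumab. Section 3.2 sets it at 480 mg every 4 weeks, up to 2 years from the start of treatment.

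Footnote c of the study calendar (Section 4.3) repeats the rule without naming events or grades and adds a start time: three weeks after the fourth dose, "or after Day 113 if the 4th dose of induction therapy has not been administered due to treatment delays or the discontinuation of combination" therapy for mainly ipilimumab-related effects.

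Section 3.4.6 opens with "Treatment with nivolumab and ipilimumab should be permanently discontinued for any of the following". Its list includes "Grade 3 drug-related uveitis, pneumonitis, bronchospasm, diarrhea, colitis, neurologic toxicity, hypersensitivity reaction, or infusion reaction of any duration requires discontinuation". It also includes any Grade 4 drug-related event, apart from amylase or lipase changes without pancreatitis and corrected electrolyte abnormalities, and liver tests above stated limits. On time, it says "If treatment is delayed > 6 weeks, the subject must be permanently discontinued from study therapy, except as to allow for prolonged steroid tapers". A separate allowance covers interruptions longer than 6 weeks for reasons unrelated to the drugs.

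Section 3.4.5 sets the condition for restarting: "Drug-related pulmonary toxicity, diarrhea, or colitis, must have resolved to baseline before treatment is resumed".

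**The concern.** Both sections are written as instructions, and neither cites the other or says which prevails. Two investigators who each follow the text could treat the same patient in opposite ways. One would stop all study drug for good. The other would start nivolumab maintenance after a serious immune-related bowel event.

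That is first a patient-safety matter. Section 2.1 states that there is no earlier experience with SBRT given concurrently with these drugs in this population, and Section 3.9 anticipates "increased incidence of colitis if normal bowel is included in irradiated abdominal fields". It is also a matter of consistency: nivolumab exposure, and through it duration of response, PFS and late adverse events, would depend on which section a site happened to follow.

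**Working it through.** The plan states no figure on this point to reproduce. The check compares the sections and then does some simple counting.

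**1. The two rules by event (drug-related, during induction, combination stopped before dose 4)**

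| Event | 3.4.3 and footnote c | 3.4.6 | Compatible? |
|---|---|---|---|
| Grade 2 diarrhea or colitis, resolved to baseline | Start nivolumab | Not listed by grade | Yes, through 3.4.5 |
| Grade 3 diarrhea or colitis | Start nivolumab | Stop both drugs, any duration | No |
| Grade 4 diarrhea or colitis | Start nivolumab | Stop both drugs; exceptions do not apply | No |
| Hepatitis below the 3.4.6 liver limits and not Grade 4 | Start nivolumab | Laboratory change alone does not require stopping | Yes, through 3.4.5 |
| Hepatitis above those limits | Start nivolumab | Stop both drugs | No |

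The protocol does not define *high grade*. Taken as Grade 3 or more, high-grade diarrhea always falls in an incompatible row. Colitis and hepatitis carry no grade in 3.4.3, so they conflict only in part.

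**2. Could 3.4.6 mean the combination only?** Its opening names both drugs. It has no tier that stops ipilimumab alone and no exemption for maintenance. Its last item concerns an event that "presents a substantial clinical risk to the subject with continued nivolumab or ipilimumab dosing". The *or* there is not decisive, but nothing in the section limits it to the combination.

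**3. How many patients?** Input: Table 2 in Section 1.4, nivolumab 3 mg/kg plus ipilimumab 1 mg/kg arm, Grade 3/4 GI disorder in 1 of 47.

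- Rate: 1/47 = 0.0213; exact 95% CI 0.0005 to 0.1129.
- Expected among 25: 25 × 0.0213 = 0.53 (0.01 to 2.8).
- Chance of at least one among 25: 1 − (46/47)^25 = 0.42 (0.013 to 0.95 at the CI limits).
- Grade 3/4 hepatic events, same table: 2/47, so 25 × 2/47 = 1.06 (0.13 to 3.6). Only the part above the 3.4.6 limits conflicts.

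These rates cover all treatment time. The documents do not give the share falling before the fourth induction dose, so the numbers that matter here are lower by an unknown amount.

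**4. Day 113 against the 6-week limit.** Induction doses fall on Day 1 of Weeks 1, 4, 7 and 10, which is Days 1, 22, 43 and 64. With earlier doses on schedule, and delay counted from the next due dose:

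| Last dose given | Next due | 6-week limit reached | Day 113 minus due date |
|---|---|---|---|
| 1 | Day 22 | 22 + 42 = Day 64 | 91 days |
| 2 | Day 43 | 43 + 42 = Day 85 | 70 days |
| 3 | Day 64 | 64 + 42 = Day 106 | 49 days |

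All three exceed 42 days. Earlier delays change this, because 3.4.5 moves later timepoints. If dose 2 slips to Day 43, dose 3 falls on Day 64 and dose 4 is due on Day 85; then 113 − 85 = 28 days, within the limit.

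**The case against.** The strongest reply is that 3.4.3 is the specific rule for ipilimumab-attributed toxicity and 3.4.6 the general one, so 3.4.3 works as an exemption: drop ipilimumab, keep nivolumab. That is a plausible intent, but no text says so, and 3.4.6 as written forbids it. The GI and hepatic algorithms in Appendix 2 are figures not available here and may show which rule was meant. Even so, the two body sections would still disagree.

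Several stronger readings are tempting, and the documents do not support them.

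- *Every start after Day 113 breaches the 6-week limit.* This holds only with earlier doses on time. The steroid-taper exception also fits many of these patients, since Appendix 2 describes corticosteroids as a primary treatment for such events. Section 3.4.3 and its figure note do not clearly impose the wait after discontinuation; footnote c does.
- *Section 3.4.3 allows nivolumab before the bowel event has resolved.* Section 3.4.5 already requires a return to baseline and is not limited to induction. Not repeating it is a matter of drafting.
- *Section 3.4.6 is the only stopping text for nivolumab.* Sections 2.8 and 3.4.7 also contain stopping rules, though neither settles this conflict.
- *SBRT will multiply the rate.* No source gives a factor. Section 3.9 ties added colitis to bowel in the field, and Section 2.1 prefers lung, mediastinum or bone as targets. In the same-dose arm, Section 1.4 reports Grade 3–4 diarrhea in 1 of 47 and places Grade 3–4 colitis only in the other dose arm.

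**Conclusion.** The conflict is real for drug-related diarrhea or colitis of Grade 3 or higher in induction, and for hepatitis above the 3.4.6 limits. It rests on reading *high grade* as Grade 3 or more, and on the body text alone. Grade 2 events that resolve to baseline are handled consistently.

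The size is small: about 0.5 of 25 patients for GI events, with a wide interval, and fewer when restricted to induction. A reader might infer that the trial's decision rules are compromised; they are not. A patient with such an event already counts in the run-in and in the Bayesian toxicity monitoring, whichever section is then followed. The rule of 17 responses in 25 could move only by the affected patient or patients. The case for correcting the text is contradictory dosing instructions for a serious toxicity.

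The Day 113 point is secondary and conditional: with on-time earlier doses, footnote c's start falls 49, 70 or 91 days after the next due dose, past the limit unless the steroid-taper or non-drug exception applies.

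**What to change.** Choose one rule and write it in every place concerned.

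- **Default, the stricter rule.** In 3.4.3 and footnote c add: *maintenance dosing will begin only if no Section 3.4.6 discontinuation criterion has been met and the Section 3.4.5 criteria to resume are met*. Delete *high grade* from 3.4.3.
- **Alternative, if nivolumab alone after Grade 3 ipilimumab-attributed toxicity is intended.** Add an ipilimumab-only tier to 3.4.6 that names the events and grades, consistent with the Appendix 2 algorithms.
- **In either case.** State that maintenance may start once the resume criteria are met, or that the wait to Day 113 does not count toward the 6-week limit.

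The cost is one amendment and a site notice, with no change to sample size, analysis or data collection. Under the default, a few patients who might have received maintenance nivolumab would lose access to it. The sponsor should weigh that when choosing between the two.

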3.4.4 Dose Modifications for Nivolumab and Ipilimumab

Dose reductions or dose escalations of nivolumab or ipilimumab are not permitted.

3.4.5 Criteria to Resume Treatment on Nivolumab and Ipilimumab

If the criteria to resume treatment are met, the subject should restart treatment at the next scheduled timepoint per protocol. However, if the treatment is delayed past the next scheduled timepoint per protocol, the next scheduled timepoint will be delayed until dosing resumes. If treatment is delayed > 6 weeks, the subject must be permanently discontinued from study therapy, except as specified in discontinuation section.

Subjects may resume treatment with study drug when the AEs resolve to Grade ≤ 1 or baseline value, with the following exceptions:

- Subjects may resume treatment in the presence of Grade 2 fatigue
- Subjects who have not experienced a Grade 3 drug-related skin AE may resume treatment in the presence of Grade 2 skin toxicity
- Subjects with baseline Grade 1 AST/ALT or total bilirubin who require dose delays for reasons other than a 2-grade shift in AST/ALT or AST/ALT or total bilirubin
- Subjects with combined Grade 2 AST/ALT AND total bilirubin values meeting discontinuation parameters should have treatment permanently discontinued.
- Drug-related pulmonary toxicity, diarrhea, or colitis, must have resolved to baseline before treatment is resumed.
- Drug-related endocrinopathies adequately controlled with only physiologic hormone replacement may resume treatment.

3.4.6 Discontinuation Criteria for Nivolumab and Ipilimumab

Treatment with nivolumab and ipilimumab should be permanently discontinued for any of the following:

If treatment is delayed > 6 weeks, the subject must be permanently discontinued from study therapy, except as to allow for prolonged steroid tapers to manage drug-related adverse events. Prior to re-initiating treatment in a subject with a dosing interruption lasting > 6 weeks, the overall PI ([name]) must be consulted. Tumor assessments should continue as per protocol even if dosing is interrupted.

Dosing interruptions > 6 weeks that occur for non-drug-related reasons may be allowed if approved by the Investigator. Prior to re-initiating treatment in a subject with a dosing interruption lasting > 6 weeks, the Investigator must be consulted. Tumor assessments and

the collection of blood and tissue samples for correlative studies should continue as per protocol even if dosing is interrupted. Radiation treatment should continue if the treatment is unlikely to worsen the adverse event.

- Any Grade 2 drug-related uveitis or eye pain or blurred vision that does not respond to topical therapy and does not improve to Grade 1 severity within the pre-treatment period or requires systemic treatment
- Any Grade 3 non-skin, drug-related adverse event lasting > 7 days, with the following exceptions for drug-related laboratory abnormalities, uveitis, pneumonitis, bronchospasm, diarrhea, colitis, neurologic toxicity, hypersensitivity reactions, and infusion reactions:
 - Grade 3 drug-related uveitis, pneumonitis, bronchospasm, diarrhea, colitis, neurologic toxicity, hypersensitivity reaction, or infusion reaction of any duration requires discontinuation
- Grade 3 drug-related laboratory abnormalities do not require treatment discontinuation except:
 - Grade 3 drug-related thrombocytopenia > 7 days or associated with bleeding requires discontinuation
 - Any drug-related liver function test (LFT) abnormality that meets the following criteria require discontinuation:
 - AST or ALT > 8 x ULN
 - Total bilirubin > 5 x ULN
 - Concurrent AST or ALT > 3 x ULN and total bilirubin > 2 x ULN
- Any Grade 4 drug-related adverse event or laboratory abnormality, except for the following events, which do not require discontinuation:
 - Grade 4 amylase or lipase abnormalities that are not associated with symptoms or clinical manifestations of pancreatitis.
 - Isolated Grade 4 electrolyte imbalances/abnormalities that are not associated with clinical sequelae and are corrected with supplementation/appropriate management within 72 hours of their onset
- Any adverse event, laboratory abnormality, or intercurrent illness which, in the judgment of the Investigator, presents a substantial clinical risk to the subject with continued nivolumab or ipilimumab dosing

